### 9.2.3 Secondary Endpoints

9.2.3.1 TB treatment outcomes: mycobacterial culture conversion at week 8, occurrence of TB treatment failure at or after week 24, and occurrence of TB relapse/recurrence by week 72.

NOTE A: TB treatment outcomes for participants who enroll with probable TB for whom week 8 mycobacterial culture conversion cannot be assessed will include week 8 AFB smear conversion coupled with resolution of signs, symptoms, and radiographic abnormalities on which the diagnosis of probable TB was based or solely resolution of signs, symptoms, and radiographic abnormalities for participants with negative AFB smears or AFB smears that are not available at baseline, in addition to TB treatment failure at or after week 24, and TB relapse/recurrence by week 72.

NOTE B: Participants who cannot produce sputum even with induction, as noted on the CRF, will be considered MTB culture negative and AFB smear negative in analyses.

9.2.3.2 HIV virologic suppression based on two definitions: plasma HIV RNA level  $< 400$  copies/mL at 48 weeks and  $< 50$  copies/mL at 48 weeks.

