### 1.3 Secondary Objectives

- 1.3.1 To evaluate TB treatment outcomes (as measured by week 8 mycobacterial culture conversion, treatment failure at or after week 24, TB relapse/recurrence by week 72) between RBT-containing arms and the RIF-containing arm, to include the association between RBT or RIF exposure as well as other factors potentially associated with outcomes of TB treatment.

NOTE: TB treatment outcome measurements for participants who enroll with probable TB for whom week 8 mycobacterial culture conversion rates cannot be assessed will include either week 8 AFB smear conversion rate coupled with resolution of signs, symptoms, and radiographic abnormalities on which the diagnosis of probable TB was based or solely resolution of signs, symptoms, and radiographic abnormalities for participants with negative AFB smears or AFB smears that are not available at baseline; in addition, TB treatment failure at or after week 24, and TB relapse/recurrence by week 72 will be captured as TB outcome measures.

- 1.3.2 To compare rates of virologic suppression to < 50 copies/mL at 48 weeks for the two standard dose LPV/r and RBT arms versus the double-dose LPV/r and RIF arm.
- 1.3.3 To compare rates of virologic suppression to < 50 copies/mL and < 400 copies/mL at 48 weeks for standard dose LPV/r and RBT versus standard dose LPV/r, RBT, and RAL.
- 1.3.4 To compare safety and tolerability during TB treatment of double-dose LPV/r and RIF between the three treatment arms.
- 1.3.5 To compare the proportion of participants with virologic failure and time to virologic failure between the three treatment arms.

- 1.3.6 To compare the emergence of HIV-1 drug resistance mutations in gag, protease, reverse transcriptase (RT), and integrase in participants with virologic failure between the three treatment arms.
- 1.3.7 To compare the proportion of participants with TB drug-resistance among cases of TB treatment failure and relapse/recurrence of TB between the three treatment arms.
- 1.3.8 To characterize TB immune reconstitution inflammatory syndrome (IRIS) events.
- 1.3.9 To compare changes in CD4+ T-cell count, and proportion of participants who experience new AIDS-defining illness, HIV disease progression (defined as new AIDS-defining illness or death), or death between the three treatment arms.

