#### 6.2.6 Time of Suspected TB Treatment Failure or Recurrence

A participant must undergo the evaluations indicated in the SOE under TB treatment failure or recurrence within 28 days of the site becoming aware of a possible TB treatment failure or recurrence of TB disease as indicated below. TB treatment failure should be suspected for participants who have not resolved their signs and symptoms related to the qualifying episode of TB or have a persistently positive AFB smear in sputum or other body fluid or tissue sample after completion of the intensive phase of TB treatment. TB treatment failure is confirmed if a TB-positive mycobacterial culture is obtained from any site after week 16 of TB treatment.

Participants who have resolved their signs and symptoms related to the qualifying episode of TB and have negative AFB smears and mycobacterial cultures, if available, but have a recurrence of signs or symptoms of TB at any time at or after week 24 and before the week 72 endpoint should return for an interim visit as soon as possible after presentation. A sputum sample should be obtained for AFB smear and culture, and a chest x-ray or other radiographic evaluation as indicated should be performed. Any results from repeated sputum and chest x-ray evaluations must be documented. If the participant enrolled with exclusively extrapulmonary TB and no new pulmonary signs or symptoms are present, a sputum sample is not required, but a specimen from any clinically relevant extrapulmonary site, if available (e.g., pleural, pericardial, or peritoneal fluid or tissue biopsy; aspirate of lymph node, cold abscess, bone marrow or joint fluid; cerebrospinal fluid; liver, bone marrow or other tissue biopsy or; blood) should be submitted for AFB smear, mycobacterial culture, and TB drug susceptibility testing. Any information that is provided by the local TB clinic related to TB recurrence must be recorded on the CRFs when received, as noted for TB evaluations above. Any positive sputum or other body fluid or tissue culture should be stored at the site or in the local TB laboratory as appropriate to site procedures.

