#### Entry and Subsequent Sputum Collections

At entry (not required if obtained within 3 days prior to entry), week 8, week 12, and at the time of suspected TB treatment failure/TB recurrence, participants will be given sterile collection containers to collect first morning expectorated sputum the day of their clinic visit. These specimens will be collected by induction if they cannot be spontaneously produced.

Sputum will be collected as described below:

- If the final dose of intensive phase of INH, RIF or RBT, EMB and PZA coincides with the week 8 visit, collect sputum samples within 72 hours of ingestion of the final dose of intensive phase of TB treatment and prior to the ingestion of the second dose of continuation phase TB medications.
- If the final dose of intensive phase INH, RIF or RBT, EMB and PZA does NOT coincide with the week 8 visit, (a) collect a sputum sample at week 8, and (b) schedule a separate visit within 72 hours of ingestion of the final dose of intensive phase of TB treatment and prior to the ingestion of the second dose of continuation phase TB medications.

- From week 16 onward, collect single sputum samples every 4 weeks (monthly) for smear and cultures if sputum culture results have not demonstrated two consecutive TB-negative cultures after week 12, and discontinue monthly smear and cultures once there are two consecutive TB-negative sputum cultures. Drug susceptibility testing on available samples should be done if the sputum culture remains MTB positive after the week 8 timepoint.

If the sputum sample does not become TB-negative by the week 16 time point, the participant has failed TB treatment. The participant will be taken off study TB medications and will be treated for possible drug-resistant TB at the discretion of the primary clinician according to local, national, or international guidelines used for treatment of drug-resistant TB. These participants will be followed on study, but off study-provided TB drugs until week 72. If the participant must discontinue study-provided TB treatment, he/she may still continue to take study-provided ARVs.

Collect sputum in a sterile single-use collection container. If possible, the oral cavity should be rinsed with clean water that is expectorated prior to giving the sample. The specimen should contain 3-5 mL of sputum.

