**6.3.7 TB Treatment Status and Outcome Determination**

At completion of the entire course of TB treatment, TB treatment status/outcome must be recorded on the CRF, and should also be documented again at weeks 48 and 72, at the time of detection/diagnosis of TB treatment failure or TB relapse/recurrence or at the time of premature discontinuation or death.

TB treatment status/outcome will be classified according to the following, adapted from ATS guidelines.

**Cure:** Completion of all recommended doses of medication *and* 2 consecutive TB-negative mycobacterial cultures.

**Treatment failure:** TB-positive mycobacterial culture after 16 weeks of TB treatment for a participant who was documented to be taking TB medications.

**Died:** Participant who died for any reason before the completion of TB-treatment.

**Default:** Participant whose TB-treatment was interrupted for 2 or more consecutive months and did not reinitiate TB therapy.

**Transfer out/lost to follow-up (LTFU):** Participant who was transferred to another treatment facility or LTFU and for whom the TB treatment outcome is not known.

**Treatment ongoing:** At time of evaluation, participant is still undergoing treatment for TB. Documentation should be made of why prolonged TB treatment is occurring, including: default with reinitiation of TB treatment, initial TB treatment failure, and persistent TB-positive mycobacterial cultures.

**Relapse/recurrence:** Participant who has 2 consecutive TB-negative mycobacterial cultures and who subsequently has clinical or radiographic deterioration consistent with active TB at or after week 24 and before the week 72 endpoint.

**Treatment completed:** Participant who has completed TB treatment but who does not meet the criteria to be classified as a cure or a failure.

**NOTE:** For participants who are enrolled with probable TB and do not have a positive mycobacterial culture from any site available to meet these outcome definitions, but who have specimens with a positive AFB smear, the AFB smear result will be substituted for the mycobacterial culture result in assessing TB outcomes. If there are no positive AFB smear results, then the assessment of TB outcomes will be based on best clinical judgment and further reviewed by the team and an independent endpoint reviewer.

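### TB treatment failure counts in endpoint 9.2.3.1 only from week 24, but the protocol's own rules declare it from about week 16, and nothing says whether a failure in between is scored

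*Protocol*

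**What the plan says.** The endpoint and its objective use a week-24 limit:

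- Protocol 9.2.3.1 has three components: "mycobacterial culture conversion at week 8, occurrence of TB treatment failure at or after week 24, and occurrence of TB relapse/recurrence by week 72". The week-24 limit is repeated in Note A for participants enrolled with probable TB.
- Objective 1.3.1 uses the same limit: "treatment failure at or after week 24, TB relapse/recurrence by week 72".

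The sections that define failure use week 16:

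- 6.3.2, on sputum collection: "If the sputum sample does not become TB-negative by the week 16 time point, the participant has failed TB treatment". It continues: "The participant will be taken off study TB medications and will be treated for possible drug-resistant TB". The participant stays in follow-up to week 72. Monthly cultures run from week 16, with the instruction to "discontinue monthly smear and cultures once there are two consecutive TB-negative sputum cultures".
- 6.2.6: "TB treatment failure is confirmed if a TB-positive mycobacterial culture is obtained from any site after week 16 of TB treatment".
- 6.3.7 defines the failure category as "TB-positive mycobacterial culture after 16 weeks of TB treatment for a participant who was documented to be taking TB medications". The outcome is recorded when the TB course is completed, and it "should also be documented again at weeks 48 and 72, at the time of detection/diagnosis of TB treatment failure".

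Three other provisions matter. Exclusion 4.2.4 allows up to 28 cumulative days of TB treatment before entry. Endpoint 9.2.3.5 and objective 1.3.7 look at drug resistance among TB treatment failures and relapses with no week limit. Section 9.6.3 treats the secondary analyses as exploratory.

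**The concern.** The protocol can declare that a participant has failed TB treatment, change that participant's TB treatment as a result, and then leave the failure out of the endpoint named for it. The change of treatment makes later negative cultures plausible, so this pattern is not far-fetched.

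TB outcome on rifabutin versus rifampin is the first secondary objective. An analyst working from 6.2.6 or 6.3.7 and one working from 9.2.3.1 could report different failure counts from the same records, each with text to support the choice.

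**Working it through.** The protocol gives no failure rate or power figure for this endpoint, so there is none to reproduce. The check sets the definitions side by side, follows three culture histories through them, and does the week arithmetic.

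**Culture histories.** Assume no TB treatment before entry, nominal visit dates, TB medications being taken, and the natural reading of 9.2.3.1.

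| Culture results by study week | Failure under 6.2.6, 6.3.2, 6.3.7 | Scored in 9.2.3.1 |
|---|---|---|
| Positive at 8, 12, 16, 20; negative at 24, 28 | Yes: 6.3.2 at week 16; 6.2.6 and 6.3.7 at week 20 | Week-8 non-converter only; the failure is not scored |
| Negative at 8; positive at 20; negative at 24, 28; no later deterioration | Yes: 6.2.6 and 6.3.7 at week 20 | In none of the three components |
| Positive at 8 and still positive at 24 | Yes | Week-8 non-converter and failure |

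The relapse component does not rescue the first two rows. In 6.3.7, relapse needs two consecutive negative cultures followed by clinical or radiographic deterioration from week 24 on. In both rows monthly cultures may stop after week 28, because two consecutive negatives have been seen.

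**Length of the gap.** Let d be the weeks of TB treatment before entry, from 0 to 4 (28 days / 7, from 4.2.4), so that treatment week = study week + d. The rule in 6.2.6 and 6.3.7 opens after study week 16 − d.

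1. If week 24 in 9.2.3.1 is a study week, the gap is 24 − (16 − d) = 8 + d. That is 8 weeks at d = 0 and 12 weeks at d = 4. The scheduled monthly cultures strictly inside it are week 20 (d = 0), or weeks 16 and 20 (d = 4).
2. If week 24 is a week of TB treatment, it falls at study week 24 − d, and the gap is (24 − d) − (16 − d) = 8 weeks. At d = 4 it runs from study week 12 to study week 20, and the only monthly culture strictly inside is week 16.
3. At d = 4, study week 20 is treatment week 20 + 4 = 24. A positive culture at that visit is scored on the treatment clock and not on the study clock.

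These are nominal figures. They ignore the ±7-day visit window and the 72-hour window for starting TB treatment. They also take prior treatment as cumulative days; if it was interrupted, calendar time since the first dose could be longer.

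**The week-16 rules against each other.** Section 6.3.2 works by the week 16 time point; 6.2.6 and 6.3.7 work after week 16 of treatment. With no prior treatment, a positive culture exactly at week 16 in a participant who has never converted is a failure under 6.3.2 alone. A visit a few days late could meet all three.

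**The case against.** The best defence is that the week-24 limit describes when status is assessed, not when failure occurs. Section 6.3.7 has outcome recorded at completion of the course (at least 24 weeks) and again at weeks 48 and 72. A participant with a positive culture after 16 weeks of treatment still fits the failure wording when classified then. The same section names initial treatment failure as a reason to document when treatment is still ongoing, so early failures remain visible. This reading is reasonable and has some textual support. No passage states it, however, and 9.2.3.1 speaks of the occurrence of failure from week 24. The defence lowers confidence that such failures would be dropped; it does not remove the need to say which is meant.

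The practical effect is also limited, and these points stand. A participant who never converts would normally be counted at week 8. The failure is recorded under 6.3.7 when diagnosed, so no data are lost. Interim TB monitoring in 9.5.2 uses the cure rate, not this endpoint. SAP 1.6 says accrual period 2 will not open, so with 60 planned participants any such case could be listed individually.

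A reader might also infer that 9.2.3.5 contradicts 9.2.3.1 because their counts would differ. That does not follow: 9.2.3.5 covers failures and relapses together, so its total need not equal the failure count under any wording. The narrower point is that the failures entering 9.2.3.5 should be the same set as those in 9.2.3.1.

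**Conclusion.** The mismatch is real and worth correcting. As worded, 9.2.3.1 can leave out failures that the protocol itself declares, over a nominal gap of 8 to 12 weeks, and one culture pattern escapes all three components. This rests on the natural reading of the week-24 limit; carrying earlier failures forward to a later assessment is possible but unstated.

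A reader might go further and infer that the rifabutin versus rifampin comparison is biased. The documents do not support that. They give no rate of failure in the gap and no rate of later conversion, and nothing shows that either would differ by arm. No bias, direction or loss of power can be computed, and 9.6.3 makes the analysis exploratory. Nor is the SAP's silence evidence of an omission: SAP 1.1 confines that plan to the PK and safety interim report.

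**What to change.** Limit the change to the endpoint wording:

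1. In 1.3.1 and 9.2.3.1, including Note A, state that every TB treatment failure declared under the protocol's definition counts, whatever TB treatment follows. The note under 9.2.3.4, which applies the virologic failure definition whether or not randomized ART is being taken, is a model.
2. Tabulate failures before week 24 and from week 24 on, by arm.
3. State whether weeks run from study entry or from the start of TB treatment, given the prior treatment that 4.2.4 allows.
4. Use the same set of failures for the failure part of 9.2.3.5.

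Separately, flag to the sponsor that the week-16 wording in 6.3.2 and that in 6.2.6 and 6.3.7 must be reconciled. The 6.3.2 rule also governs stopping study TB drugs, so this review takes no position on which is right.

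The cost is a few sentences. No new data are needed, because 6.3.7 already has the outcome documented when failure is diagnosed. The drawback is that early and late failures are combined in one count; the tabulation in step 2 answers this and keeps the week-24 count, as now worded, in view.

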### 9.2.3.3 Safety and tolerability:

9.2.3.3.1 Highest reported grade of each new Grade 3 or 4 laboratory value or sign or symptom that is at least a one grade increase from baseline.

9.2.3.3.2 Ordered categorical variable indicating most stringent level of ARV drug management due to toxicity that was required over the co-treatment period: premature permanent treatment discontinuation; treatment hold for more than 3 consecutive days; and none of the above.

9.2.3.3.3 Ordered categorical variable indicating most stringent level of TB drug management due to toxicity that was required over the co-treatment period: premature permanent treatment discontinuation; treatment hold for more than 7 consecutive days; and none of the above.

9.2.3.4 HIV virologic failure is defined as two consecutive plasma HIV-1 RNA levels  $\geq$  1000 copies/mL at or after 16 weeks and before 24 weeks of ART or  $\geq$  400 copies/mL at or after 24 weeks of treatment.

NOTE: This definition of virologic failure will be applied regardless of whether or not randomized ART is being taken at the time of failure.

9.2.3.4.1 Occurrence of HIV virologic failure.

9.2.3.4.2 Time to HIV virologic failure.

9.2.3.5 TB drug resistance patterns in participants who have TB treatment failure or relapse/recurrence of TB.

9.2.3.6 Occurrence of MTB IRIS events.

9.2.3.7 Predictors of disease progression:

9.2.3.7.1 CD4+ T-cell counts at baseline and at weeks 8, 24, 48, and 72.

9.2.3.7.2 Occurrence of new AIDS-defining illnesses.

9.2.3.7.3 Occurrence of HIV-disease progression (defined as new AIDS-defining illness or death).

9.2.3.7.4 Occurrence of death.

9.2.4 Additional endpoints for supportive/exploratory analyses that will be defined in more detail in separate analysis plans:

9.2.4.1 HIV-1 drug resistance patterns in participants who have HIV virologic failure.

9.2.4.2 LPV plasma concentrations in Arm B, RBT plasma concentrations in Arms A and C, and RAL plasma concentration in Arm C at weeks 2 and 8 in accrual period 2 participants.

9.2.4.3 Cost-benefit measures related to adding RAL.

